Title: Comparative effects of integrated physical training with high protein diet versus low protein diet in COVID-19 asymptomatic older adults with Sarcopenia symptoms.

Clinical trial registration number: NCT05224453

Date: 12/02/2022

Study Protocol

Background: Sarcopenia is the major health concern and common consequence of COVID-19 in the aging population. Moreover, this clinical condition has not been considered in usual physical rehabilitation practice and nor its optimal protein requirement in food is well defined, which requires a meaningful study in this field.

Objective: To find and compare the clinical and psychological effects of integrated physical training with a high protein diet versus low-protein diet in community dwelling COVID-19 asymptomatic older adults with Sarcopenia symptoms.

Design: It is a single-blinded, randomized, experimental study performed during March -2020 to November-2021. The trial received acceptance from the department of ethical committee (DEC), Prince Sattam bin Abdulaziz University, Al-Kharj, Saudi Arabia with an approval number of RHPT/020/51. The DEC approved the subject consent form, treatment protocols and the outcome parameters measured in the trial. The trial was executed in accordance with the ethical guidelines laid down in the 1964 Declaration of Helsinki and was registered in the clinical trial registry with registration number NCT05224453. The finally selected subjects for the trial were asked to fill the written subject consent form and underwent measurements for pre interventional personal and anthropometric data. A two block simple random sampling method was used to randomize and allocated the participants into two treatment groups. The group A was treated with integrated physical training with high protein diet (n = 38) and the group B was treated the same integrated physical training with low protein diet (n = 38) for a duration of eight weeks.

Subjects

Subjects for the study were received from local and government hospitals in Al-Kharj and Riyadh region of Saudi Arabia. Positively diagnosis of asymptomatic COVID-19 male patients

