with 60 – 80 years of age was recruited for the study. Appendicular skeletal muscle mass index (ASMI < 7.0 kg/m²) was used to identify sarcopenia (skeletal muscle loss). Sarcopenia was diagnosed according to the guidelines given by the Asian working group for Sarcopenia (AWGS). Patients with less muscle mass, low hand grip strength (< 24 kg) and decrease walking speed (< 0.7 m/sec) were involved. Subjects with a history of physical workout, taking medicines, recent surgeries and joint problems in leg, heart and lung problems, neurological issues, any other systemic diseases and contraindications for physical training were eliminated from the study. The fig-1 depicts the methods and procedure of involving study subjects in this trial.

Intervention

Subjects in group-A and Group-B (n=38) underwent integrated physical training for 8 weeks. A trained physiotherapist executed the training protocols under proper COVID instructions. The training protocol was recorded in treatment logbook and was assessed each session by the study supervisor. Prior to the start of exercise training, the basic tests such as; body temperature, blood-pressure, oxygen saturation rate, heart beat and physical fitness were recorded. If these scores exceeded the normal values such as, like body temperature > 38.0°C, blood-pressure > 150/100mmHg and heart beat >90 beat per min or < 50 beat per min, subjects were asked to refrain from training on that session.

The maximum heart rate (MHR) was used to measure the intensity of the given exercise. It was found by reducing the subject's age from number 220. Aerobic training was given with 40 to 50 percent of maximum heart rate for all the subjects, which is considered as low-intensity aerobic training (LAT). Every day, the intervention started with 10mins of stretching of upper and lower limb muscles. Subsequent to stretching, the subjects were asked to do 30 mins of LAT; consisting of 20 mins of treadmill (Axos, Kettler Runner, China) and 10 mins of cycle ergometer (Axos, Kettler Runner, China), then with 10 mins of cool down.

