All the participants, in both the groups, were prescribed with strength training exercises with resistance depends upon each subject's individual muscle assessment. The ideal resistance for each muscle groups were measured based on 1 repetition maximum (1RM) principle. The important muscle groups in the spine, upper and lower limb were trained. Each muscle group was undergone training for 3 sets consisting 10 repetitions in each set, with a relaxation of 5 mins rest between sets. The weight was gradually increased as per the subject and therapist needs and the exercise was performed for 4 days in a week for 8 weeks.

In addition to the integrated physical training exercises, group A received a high protein diet in the range of 1.1 – 1.3 g/kg protein/ ideal body weight/day (>1 g/kg aBW/d) and group B received low protein diet in the range of 0.7 – 0.9 g/kg protein/ ideal body weight/day (<1 g/kg aBW/d) as prescribed by a qualified nutritionist.

Outcome measures

Hand grip strength: The test is easy to perform and a less expensive one. It measures the strength of upper extremity by using a device handheld dynamometer. The participant was instructed to press the hand piece of the dynamometer to the maximum of his ability and the values shown on the display were recorded. Three values were noted for each participant and the mean value was considered for interpretation and it is a reliable and valid tool to measure the strength of upper extremity.

Muscle cross sectional area - CSA: Muscle CSA is measured with Magnetic resonance imaging (MRI) scan and it is an expensive measurement. The CSA of three major muscle such as; half way at arm - biceps, thigh - quadriceps and calf muscles were measured and included for analysis.²³

Kinesiophobia: TSK – 11; Tampa scale of kinesiophobia questionnaire was administered to find the level of fear of movement of participants. The questionnaire has eleven items, which measures the mindset at various activities in four point likert scale. Maximum score indicates high level of fear whereas the minimum score indicates low level of fear during activities.

Quality of life: Sarcopenia quality of life (SarQol) questionnaire was used to measure the subjects' wellbeing. The participants filled the questionnaire themselves and it is a robust tool to measure Qol.

Sample size

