The sample size for the study was decided based on the report from the study by Yoo Jet al. Thirty-five subjects in each group were found by assuming forty percentage mean improvement in handgrip strength with standard deviation of 2. By accepting 10% drop of subjects at 6 month follow up, two subjects were added in each group. Hence, N=76 subjects were selected and divided into two groups with n=38. The sample size was calculated with the statistical power at 80% with α level of 0.05. The whole analysis was done with G*Power - version 3.1.9.7 software.

Statistical analysis plan

Subjects' personal and anthropometric measurements were calculated through Kolmogorov–Smirnov test for testing homogeneity and the data were represented in tabular form. The measurements were taken before intervention, during intervention at 4 weeks, after intervention at 8 weeks and after 6 months follow up. The data were shown as mean and standard deviation with 95% confidence interval (CI) with upper and lower limit. The time and group (4 × 2) multiple analysis of variance (MANOVA) of primary and secondary variables are reported between group A and group B at various intervals. Student's t test was used to calculate inter-group effects and repeated measures (rANOVA) was used to calculate the intra-group effects. IBMSPSS – online version 20 was used to do all the statistical tests and α level was set at 0.05.

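### Within-arm rANOVA results cannot show an effect of either regimen, and the SAP does not say that conclusions rest on the between-arm comparison alone

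*Combined protocol and SAP*

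**What the plan says.** The Statistical analysis plan section names three analyses of the outcomes:

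- a factorial analysis: "The time and group (4 × 2) multiple analysis of variance (MANOVA) of primary and secondary variables are reported between group A and group B"
- a between-arm test: "Student's t test was used to calculate inter-group effects"
- a within-arm test: "repeated measures (rANOVA) was used to calculate the intra-group effects"

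The significance level is 0.05 throughout, with sidedness not stated. There are four time points: "The measurements were taken before intervention, during intervention at 4 weeks, after intervention at 8 weeks and after 6 months follow up". The section does not say which of the three analyses decides the trial's conclusions, and it does not label the within-arm tests descriptive.

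The Objective begins "To find and compare the clinical and psychological effects of integrated physical training" and sets the high-protein diet against the low-protein diet. Under Intervention, both groups of 38 follow the same eight-week training and differ only in diet. No arm goes without training or keeps its usual diet.

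Under Subjects, grip is an entry criterion: "Patients with less muscle mass, low hand grip strength (< 24 kg) and decrease walking speed (< 0.7 m/sec) were involved". Under Outcome measures, grip is also an outcome: "Three values were noted for each participant and the mean value was considered for interpretation". The documents do not say whether the screening grip reading doubles as the baseline.

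**The concern.** The design identifies one thing: the difference between two diets given on top of the same training. A separate rANOVA in each arm asks whether that arm changed over time. The answer combines training, diet, recovery after infection, practice with the tests, and the passage of time. None of these can be separated without an arm that lacks the training or the diet. Yet the SAP calls the result an effect and tests it for significance, and the Objective speaks of finding effects as well as comparing them.

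Two things are at stake. First, the report could state that each regimen worked, for any of the four outcomes, on evidence that cannot show it. Second, because no analysis is named as decisive, nothing prevents a reader from setting one arm's within-arm p-value against the other's.

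**Working it through.** The plan gives no figure for the within-arm analysis, so there is none to reproduce. From the documents come 38 per arm, four visits, level 0.05 (two-sided assumed) and the 24 kg entry limit. All other inputs are assumptions and are marked as such.

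**1. What a within-arm change contains.** This step needs no arithmetic. Training is common to both arms, and each arm has one diet only. Change in arm A is training + diet A + recovery + practice + time. Change in arm B is the same sum with diet B. Only the difference between the arms isolates diet A against diet B. This holds for grip, muscle cross-sectional area, TSK-11 and SarQoL alike.

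**2. Regression to the mean, grip only, if screening grip is the baseline.** Assumed: normal source population with mean M, observed SD 6 kg, reliability R, selection on grip alone, no true effect.

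Expected rise = (1 − R) × 6 × φ(z)/Φ(z), with z = (24 − M)/6.

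- M = 24: z = 0, ratio 0.3989/0.5 = 0.798, gap 6 × 0.798 = 4.79 kg. At R = 0.95 the rise is 0.05 × 4.79 = 0.24 kg.
- M = 28: z = −0.667, ratio 0.3194/0.2525 = 1.265, gap 7.59 kg. At R = 0.95 the rise is 0.38 kg; at R = 0.90 it is 0.76 kg.
- M = 32: z = −1.333, ratio 0.1640/0.0912 = 1.798, gap 10.79 kg. At R = 0.85 the rise is 0.15 × 10.79 = 1.62 kg.

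In simulation with 38 men, a two-sided 5% paired test is significant in the upward direction (nominal 2.5%) in about 12% of trials in the mildest case and about 86% in the most extreme. At M = 28 and R = 0.90 to 0.95 the figure is roughly 23 to 41%. The four-visit rANOVA itself rejects in 21 to 40% at those central values.

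If baseline is measured afresh after screening, the mean rise is zero and the rANOVA returns to about 5%.

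**3. Does this bias reach the diet comparison?** No. Randomisation makes it equal in expectation in the two arms. Simulations with no diet difference (source mean 24 to 26 kg, SD 2 to 6 kg, reliability 0.80 to 0.95, common gain 0 to 2 kg) gave rejection rates of 3.8 to 6.0% for the group-by-time test and 4.2 to 5.8% for the 8-week t test.

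**4. If the two within-arm p-values were compared.** Assumed: the same true gain g (in SD) in both arms at all three post-baseline visits, visit correlation 0.7, compound symmetry.

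The visit means 0, g, g, g have a sum of squares about their mean of (0.75g)² + 3(0.25g)² = 0.75g². The noncentrality is 38 × 0.75g²/(1 − 0.7) = 95g², on 3 and 37 × 3 = 111 degrees of freedom. If p is the power in one arm, exactly one arm is significant with probability 2p(1 − p).

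| g (SD) | 95g² | p | one arm only |
|---|---|---|---|
| 0 | 0 | 5% | 9.5% |
| 0.20 | 3.80 | 33% | 44% |
| 0.25 | 5.94 | 50% | 50% |
| 0.30 | 8.55 | 67% | 44% |
| 0.40 | 15.20 | 91% | 16% |
| 0.50 | 23.75 | 99% | 2% |
| 0.70 | 46.55 | about 100% | about 0% |

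Simulation agrees closely (17% at 0.40 and 3% at 0.50).

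**The case against.** The strongest reply is that the plan already sends the diet question to between-arm tests. The rANOVA clause is the second half of a sentence whose first half plans the between-group t test, and the sentence before it plans the time-and-group MANOVA. This stands. A reader might infer that the sponsor will judge the diets by whether one arm is significant and the other is not; no text says so.

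A reader might also infer that regression to the mean could produce a spurious diet difference. It cannot do so by itself, because randomisation balances it in expectation. It concerns grip directly; muscle area could be touched only indirectly through the muscle-mass criterion, and TSK-11 and SarQoL are not entry criteria. It also needs the screening value to be the baseline, which is not stated, and averaging three readings reduces it.

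The discordance rate depends heavily on the size of the common gain. The Sample size section assumes a 40% improvement in grip with SD 2. That assumption is ambiguous, but read as a gain over an assumed baseline of 15 to 24 kg it is 0.40 × 15 = 6 kg to 0.40 × 24 = 9.6 kg, or 3 to 4.8 SD. Both arms would then be significant and discordance would be nil.

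Finally, no passage ties the finding part of the objective to the rANOVA. That is true; the link is a reading of the text. The point does not need it, because the SAP itself calls the within-arm result an effect and tests it at 0.05.

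**Conclusion.** The point holds in a limited form. The SAP plans valid types of between-arm comparison, and nothing here undermines them. The defect is that it adds an inferential within-arm test, describes the result as an effect, and does not say which result carries the conclusions. Without an untrained or usual-diet arm, a significant within-arm change cannot be credited to either regimen. That part rests on the design alone and covers all outcomes.

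The numbers are conditional. The apparent grip rise of about 0.2 to 1.6 kg, with 12 to 86% of trials showing a significant upward within-arm test under no effect, requires screening grip to be the baseline and the assumed source mean, SD and reliability. The chance that only one arm is significant runs from about 10% at zero gain, through a peak near 50% at 0.2 to 0.3 SD, to about 0% at 0.7 SD or more. It matters only if someone compares the two p-values. The documents do not support a claim that the planned diet comparison is biased. The change should be made because it is cheap and settles what the trial may conclude.

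**What to change.** - In the Statistical analysis plan section, report within-arm results descriptively: mean change with 95% CI per arm and visit, no p-value, no claim of effect.
- State that the between-arm comparison is the only basis for conclusions. Use the group-by-time contrast, which the time-and-group analysis can supply, or the baseline-adjusted between-arm difference at each visit, which would refine the planned t test.
- State whether baseline grip is measured separately from the screening reading.
- Word the Objective as a comparison of the two diets, both given with the same training.

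These are wording changes and need no new arm or larger sample. The cost is small: the sponsor gives up the claim that each programme worked, which this design could not support.
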